5.3. LIFESTYLE GUIDELINES

5.3.1. Contraception

Female subjects who are postmenopausal for at least 1 year or are surgically sterile for at least 6 weeks are considered to be of non-childbearing potential.

Female subjects of childbearing potential must agree to take appropriate precautions to avoid pregnancy from screening through 6 months after the last dose of cetuximab or through 30 days after the last dose of encorafenib or binimetinib, whichever is later.

Male subjects must agree to take appropriate precautions to avoid fathering a child and prevent exposure of seminal fluid to the partner from screening through 6 months after the last dose of cetuximab or through 90 days after the last dose of encorafenib or binimetinib, whichever is later.

The following methods are permitted under this protocol for use by the subject and his/her partner. These methods are listed below and should be communicated to the subjects and their understanding confirmed.

Methods that have been determined to be highly effective (i.e., can achieve a failure rate < 1% per year when used consistently and correctly) according to the CTFG 2014 (**Clinical Trials Facilitation Group**) include:

- Complete abstinence from heterosexual intercourse during the entire period of risk associated with the study treatments; the reliability of sexual abstinence should be evaluated in relation to the duration of the clinical trial and the preferred and usual lifestyle of the subject
- Combined (estrogen and progestogen containing) hormonal contraception associated with inhibition of ovulation:
 - Oral
 - Intravaginal
 - Transdermal
- Progestogen-only hormonal contraception associated with inhibition of ovulation:
 - Oral
 - Injectable
 - Implantable
- Intrauterine device (IUD)
- Intrauterine hormone-releasing system (IUS)
- Bilateral tubal occlusion
- Vasectomised partner (considered highly effective provided the vasectomized male has received medical assessment of surgical success and that the male is a female subject's sole sexual partner)

Acceptable birth control methods that result in a failure rate of more than 1% per year (CTFG 2014) include:

- Progestogen-only oral hormonal contraception, where inhibition of ovulation is not the primary mode of action
- Male or female condom with or without spermicide
- Cap, diaphragm or sponge with spermicide

NOTE: Due to the potential of encorafenib to induce CYP3A4, hormonal agents (including but not limited to birth control patch, vaginal ring, oral, injectable, or implanted contraceptives) are permissible only when combined with other highly effective or acceptable methods of contraception.

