1.2.2. BINIMETINIB

Chemical and pharmaceutical characteristics

Binimetinib (MEK162 or W0074) is an orally bioavailable, selective and potent mitogen-activated protein kinase kinase (MEK) 1 and MEK 2 inhibitor that is active in inhibiting phosphorylated extracellular signal-regulated kinase (pERK) and growth of *BRAF*-mutant cancer cells in the low nanomolar range.

Non-clinical data

Acute, sub-chronic, chronic and reproductive toxicity, genotoxicity and phototoxicity studies were completed in rats and monkeys to support chronic administration of binimetinib to adult subjects. There was no evidence of a genotoxic potential in vitro or in vivo. The adverse effects of MEK inhibitors in humans are similar to those observed in rats and monkeys, with the exception of ocular findings. These adverse effects include gastrointestinal intolerance and diarrhea, rash (skin findings in rats only), retinal events (only seen in humans) and retinal vein occlusion (rarely seen in humans). In vitro and in vivo phototoxicity studies conducted in mice indicate that binimetinib has a low risk of weak phototoxic potential at therapeutic doses. Furthermore, there has been no evidence of phototoxicity or photosensitivity in humans treated with binimetinib for cancer or for rheumatoid arthritis.

Given the embryo-lethal effects seen in rats and rabbits and the teratogenic effects seen in rabbits, binimetinib should not be used in pregnant women. Women of child-bearing potential must be advised to use highly effective contraception methods as described in CTFG 2014 (see **Section 5.3.1** in the protocol).

For further details, please refer to the current Binimetinib Investigator's Brochure (**Bini IB**).

Clinical Safety

As of 20 January 2018, a total of 2816 healthy subjects and patients have received at least 1 dose of binimetinib, either as a single agent or in combination with other targeted agents, standard chemotherapy agents or immunomodulating agents. These patients constitute the binimetinib safety population, which includes 229 healthy subjects, 17 subjects with hepatic dysfunction, 6 subjects with renal dysfunction, 164 patients with rheumatoid arthritis and 2400 patients with advanced cancer.

For further details, please refer to the current Binimetinib Investigator's Brochure (**Bini IB**).

Single-agent binimetinib

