- ii. Platelets $\geq 100 \times 10^9/L$.*
- iii. Hemoglobin ≥ 9.0 g/dL.*

Note: Blood transfusions are allowed provided that the subject has not received more than 2 units of red blood cells in the 4 weeks prior to achieve the minimum required hemoglobin level.

10. Adequate renal function at screening and baseline.

- i. Serum creatinine $\leq 1.5x$ upper limit of normal (ULN) or*
- ii. Calculated creatinine clearance (CrCl) ≥ 50 mL/min by Cockcroft-Gault formula*

11. Adequate electrolytes at screening and baseline, defined as serum potassium and magnesium levels within institutional normal limits.

Note: replacement treatment to achieve adequate electrolytes will be allowed

12. Adequate hepatic function at screening and baseline:

- i. Serum total bilirubin $\leq 1.5 \times$ ULN and < 2 mg/dL. Note: Total bilirubin $> 1.5 \times$ ULN is allowed if direct (conjugated) bilirubin is $\leq 1.5 \times$ ULN (and indirect (unconjugated) bilirubin is $\leq 4.25 \times$ ULN – Only applicable for France).*
- ii. Alanine aminotransferase (ALT) and/or aspartate aminotransferase (AST) $\leq 2.5 \times$ ULN, or $\leq 5 \times$ ULN in the presence of liver metastases.*

13. Adequate cardiac function at screening:

- i. Left ventricular ejection fraction (LVEF) $\geq 50\%$ as determined by MUGA scan or ECHO.*
- ii. Mean triplicate QT interval corrected for heart rate according to Fridericia's formula (QTcF) value ≤ 480 msec.*

14. Subject able to take oral medications.

15. Willing and able to comply with scheduled visits, treatment plan, laboratory tests and other study procedures.

16. Female subjects are either postmenopausal for at least 1 year, are surgically sterile for at least 6 weeks, or must agree to take appropriate precautions to avoid pregnancy.

Notes:

- (a) *Precautions to avoid pregnancy must be conducted from screening through 6 months after the last dose of cetuximab or through 30 days after the last dose of encorafenib or binimetinib, whichever is later if of childbearing potential.*
- (b) *Permitted methods of contraception as provided (in Section 5.3.1) should be communicated to the subjects and their understanding confirmed. For all females, the pregnancy test must be negative at screening and baseline.*

17. Male subject must agree to take appropriate precautions to avoid fathering a child.

Notes:

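### Protocol 5.3.1 lets women of childbearing potential rely on a condom, cap, diaphragm or sponge alone, although 1.2.2 says they must be advised to use highly effective contraception

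*Protocol*

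**What the plan says.** Protocol 1.2.2 gives the hazard first: "Given the embryo-lethal effects seen in rats and rabbits and the teratogenic effects seen in rabbits, binimetinib should not be used in pregnant women". The rule follows: "Women of child-bearing potential must be advised to use highly effective contraception methods as described in CTFG 2014", with a cross-reference to 5.3.1.

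Section 5.3.1 introduces its list with "The following methods are permitted under this protocol for use by the subject and his/her partner". The list has two groups. The first is called highly effective and defined by a failure rate under 1% per year with consistent and correct use. The second is headed "Acceptable birth control methods that result in a failure rate of more than 1% per year (CTFG 2014) include". It contains a progestogen-only pill whose main action is not to inhibit ovulation, "Male or female condom with or without spermicide", and "Cap, diaphragm or sponge with spermicide". A NOTE after the list allows hormonal agents only together with another method.

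Inclusion criterion 16 (Section 5.1) asks that women who are not postmenopausal or surgically sterile "must agree to take appropriate precautions to avoid pregnancy". Its note (b) sends sites to the list: "Permitted methods of contraception as provided (in Section 5.3.1) should be communicated to the subjects and their understanding confirmed". Section 7.2.5.1, because encorafenib may induce CYP3A4, requires at least one non-hormonal form of contraception.

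**The concern.** The background section sets a standard and names 5.3.1 as the place where it is carried out. Section 5.3.1 then permits methods that miss that standard by its own definition, and it does not say which group a woman taking binimetinib should use. Since 5.3.1 is the list to be communicated to subjects, it is the text that governs practice at a site.

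At stake is fetal exposure to a drug that the protocol says should not be used in pregnancy. Pregnancy tests at screening, baseline, Day 1 of each cycle, end of treatment and the 30-day follow-up, together with stopping treatment when pregnancy is suspected (10.4), limit how long such an exposure lasts. They do not prevent conception.

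**Working it through.** No arithmetic applies. The check sets the provisions side by side and asks whether any of them rules out a barrier method as a woman's only method.

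1. **Standard (1.2.2).** Highly effective methods are to be advised to women of childbearing potential.
2. **Definition (5.3.1).** Highly effective means under 1% failure per year. The second group is above 1% by its heading, so nothing in it is highly effective.
3. **Status of the second group (5.3.1).** It stands under the same introduction as the first, so it is permitted for the subject and the partner. No words restrict it to men or to use as an add-on.
4. **Criterion 16 (5.1).** It requires appropriate precautions and refers back to 5.3.1. It adds no threshold.
5. **NOTE (5.3.1).** It sets a combination rule for hormonal agents only. It reaches the progestogen-only pill in the second group, but not the barrier methods.
6. **Section 7.2.5.1.** It requires one non-hormonal form. A barrier method alone satisfies it.

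Applied to examples of a woman's choice:

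| Method | Permitted by 5.3.1 and NOTE | Non-hormonal form (7.2.5.1) | Highly effective by 5.3.1's definition (1.2.2) |
|---|---|---|---|
| Intrauterine device alone | yes | yes | yes |
| Combined pill alone | no | no | listed as such |
| Combined pill plus condom | yes | yes | yes, through the pill as listed |
| Condom alone | yes | yes | **no** |
| Cap, diaphragm or sponge with spermicide alone | yes | yes | **no** |

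The last two rows are the gap: each passes every operative rule and falls short of the level in 1.2.2.

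**Period covered.** The reason given in 1.2.2 concerns binimetinib. For women, 5.3.1 ties binimetinib and encorafenib to 30 days after the last dose. The longer limit, 6 months, is tied to cetuximab. The mismatch with 1.2.2 therefore covers treatment plus 30 days.

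**The case against.** The strongest reply is that the two sections do not strictly collide. Section 1.2.2 is background and sets a duty to advise. Section 5.3.1 puts the highly effective methods first and labels the rest openly by failure rate. A site can advise the first group and still permit the second. The second group also has proper uses: the list serves both sexes, male subjects must keep seminal fluid from the partner, and hormonal users need a non-hormonal method as well. Barrier-only use by women may be an unintended result of one list doing several jobs.

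Much of this stands. The groups are labelled, and the unintended-result explanation is plausible. But the restriction is not written, the section that 1.2.2 points to does not repeat its advice, and both groups are to be communicated on equal terms. If the second group was meant as an addition, the remedy only puts that meaning into words.

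Two limits on reach also stand. Enrolment has ended, since the last subject started treatment on 27 Dec 2019. And the consent forms are not among the documents reviewed.

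Stronger readings that a reader might infer are not supported:

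- *That women were misinformed.* Without the consent forms, what subjects were told cannot be judged.
- *That the interval between pregnancy tests measures the problem.* Tests fall 28 days apart, or up to 28 + 2 × 3 = 34 days using the visit window at both ends. That interval is the same whichever method a woman uses, so it says nothing about the added risk from permitting barrier methods alone.
- *That the stricter rule should run through the whole 6-month window, with a letter to sites about women long off treatment.* Beyond 30 days the window rests on cetuximab, and 1.2.2 gives no reason for a stricter rule there.
- *That the NOTE contradicts 7.2.5.1.* The NOTE lets a hormonal agent be paired with any method of either group, while 7.2.5.1 asks for a non-hormonal one. Both can be met together, and 7.2.5.1 already binds.

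**Conclusion.** The point holds as an inconsistency within the protocol that bears on subject safety. Section 5.3.1 permits, as a woman's sole method, two entries that fall below the level of contraception that 1.2.2 says must be advised, and no other section restricts them. It should be corrected, because the extension from 28 Dec 2020 keeps some subjects on the same treatment.

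Its size cannot be stated. The documents do not give the number of women of childbearing potential, how many rely on a barrier method alone, or any failure rate beyond the 1% threshold. The number affected is probably small and could be zero. The conclusion rests on the protocol text alone, and confidence is high for the mismatch only, not for any consequence in practice. It has no bearing on the endpoint, the sample size or the analysis.

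**What to change.** In 5.3.1, state that women of childbearing potential must use a highly effective method during treatment and for 30 days after the last dose of binimetinib or encorafenib. State that for them a condom, cap, diaphragm or sponge counts only as an additional method, including as the non-hormonal form that 7.2.5.1 requires. Keep condoms available to male subjects. Leave the existing 6-month window after cetuximab as it is.

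Tell continuing subjects through the written consent addendum that 9.2.1 already requires for the extension. Rewording the NOTE so that a hormonal agent must be paired with a non-hormonal method is optional alignment with 7.2.5.1.

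The cost is a few sentences in the protocol and a paragraph in the addendum. The downside is a narrower choice of sole methods for an unstated, probably small number of women.

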5.3.2. Photosensitivity

Subjects should avoid extended exposure to ultraviolet light and, when outdoors, should wear occlusive clothing, sunscreen and sunglasses while receiving encorafenib or cetuximab and for 2 months following the last dose of each agent.

5.4. NUMBER OF SUBJECTS

The target of 90 subjects with centrally confirmed $BRAF^{V600E}$ will be treated in two stages:

- First stage: 40 subjects will be treated
- Second stage: if there are at least 12 confirmed responders in the first stage, 50 additional subjects will be treated in this second stage .

In case of discordance in the results between the local assay and the central laboratory (potential false-positive local result), or lack of $BRAF^{V600E}$ confirmation, subject will be replaced.

5.5. RECRUITMENT MODALITIES

Subjects with confirmed $BRAF^{V600E}$ mCRC and who have not received any prior systemic therapy for the metastatic disease and who fulfill all inclusion and none of the exclusion criteria will be recruited.

Where authorized by local/national regulation, some specific materials may be used to improve recruitment including: leaflets, advertising in oncology journals, websites, mailing (paper or e-mail) to doctors, subject associations, and subject advocacy groups. Before use of such materials, they will be reviewed and approved by the Sponsor and submitted to and approved by the appropriate IECs/IRBs.

5.6. SUBJECTS IDENTIFICATION

The Subject's code will contain 8 digits, corresponding to the country number, the centre number and the Subject's number according to chronological order (once having signed the written informed consent).

5.7. SUBJECT DISCONTINUATION REASONS

The reasons for a subject's premature discontinuation from the study may be the following (in all cases, available data will be retained for the safety analysis):

5.7.1. Treatment Discontinuation for Individual Subject

Subjects may decide to stop participating in the study at any time for any reason without prejudice to their future medical care by the physician or at the institution. Wherever possible, the tests and evaluations listed for the End of Treatment visit and Safety Follow-up visit should be carried out and an effort should be made to continue follow-up.

If a subject decides to discontinue study treatment, he/she should be asked if he/she is willing to be contacted by telephone for monitoring of survival.

If a subject withdraws consent, the subject's data collected up to the date of consent withdrawal will be included in the analyses. The date, stated reason for and level of consent withdrawal should be documented. Any blood or tissue samples collected up to the date of withdrawal of consent will be analyzed, unless explicitly prohibited by the subject.

The Sponsor should be notified of all subjects' decision to discontinue study treatment and all study withdrawals through the designated e-CRFs in a timely manner.

Subjects meeting any of the following criteria must discontinue study drug treatment:

- **Subject decision to discontinue study treatment** (but request agreement to return for end of treatment assessments, safety follow-up assessments and/or survival follow-up).
- **Withdrawal of consent:** no further participation
- **Lost to follow up:** A subject will be considered as lost to follow up, if he/she did not attend a scheduled visit and for whom no news can be obtained after three documented attempts

with a minimum of 15 days between the first and the last attempt. This status must be dated at the latest as the database lock.

- **Investigator decision** in the subject's interest if an SAE occurs and is considered by the Investigator liable to threaten the health of the subject or if a serious disease occurs and necessitates the prescription of a medication incompatible with the pursuit of the study. The Sponsor should immediately be informed by phone or fax or email and a report explaining the discontinuation will be forwarded to him as soon as possible.
- **Progressive disease:** at any time (to be taken into account only for treatment discontinuation).
- **Unacceptable AE or toxicity** (related or not to the study treatment) or failure to tolerate the study treatment.
- **Dose interruption** of >28 consecutive days in administration of encorafenib or binimetinib, or noncompliance with study drug administration consisting of > 4 missed consecutive doses of cetuximab due to an AE or clinically significant laboratory abnormality, unless judged by the Investigator and Sponsor Medical Contact or designee to be in the best interest of the subject to continue treatment.
- **Death.**
- **Female subject becomes pregnant, or begins breastfeeding,**
- **Significant protocol deviation** that, in opinion of the investigator and/or sponsor, renders the subject unsuitable for further study drug administration.
- **Termination of the study by the sponsor.**

Subjects meeting any of the following criteria may be discontinued from study drug treatment if, during the course of the study:

- Is found to have a tumor that is *BRAF*wt by the central laboratory.
- Is noncompliant with study procedures or study drug administration in the opinion of the investigator.

5.7.2. Study Discontinuation for individual Subject

The subject may be considered discontinued from the study for the following reasons:

- Withdrawal of consent.
- Lost to follow-up.
- Death.
- Termination of the study by the Sponsor.

5.8. STUDY DISCONTINUATION

This study may be discontinued at any time due to safety concerns, failure to meet expected enrollment goals, administrative reasons or at the discretion of the Sponsor. Should the study be terminated prematurely, the Sponsor will provide written notification to all Investigators and regulatory authorities and will specify the reason(s) for early termination. The Sponsor/Investigator must inform the EC/IRB promptly and provide the reason(s) for the termination.

The Competent Authority (CA) may suspend or prohibit the study if it considers that the conditions of authorisation are not being met or has doubt about the safety or scientific validity of the study.

5.9. REPLACEMENT OF SUBJECTS

Withdrawn subjects will not be replaced.

Subjects with unconfirmed *BRAF*^{V600E} mutation will be replaced.

5.10. POST-STUDY EXCLUSION PERIOD

A post-study exclusion period is not required in this protocol.

5.11. SUBJECT CARD

As soon as consent is signed, the subject will receive from the Investigational Center a personal card to be kept throughout the study duration, which provides the following information: subject's name, Sponsor's name, study code, (if applicable) EudraCT number, complete address of the

Investigating Centre with the name and emergency phone number of the Investigator and a Sponsor 24/7 phone contact number (French and English languages).

The delivery date of the card to the study subject will be documented in the electronic case report form (e-CRF).

The preferred contact for the subject in case of need is in all cases the Investigator or his team. The card includes the name of the Investigator and the phone number which allows direct contact by the subject or the caregiver in case of need.

The card, features an additional phone number which allows, should the need arise, a contact with a Sponsor representative able to address any medical and urgent issues.

The subject is informed that, if a call is necessary, this call will be answered in English / French, which allows the subject to take any appropriate measures.

6. STUDY TREATMENT(S)

In Europe (EU), the Investigational Medicinal Product Management Service of the *Institut de Recherche Pierre Fabre (IRPF)* will supply the investigational centers with labeled and packaged encorafenib, binimetinib and cetuximab units necessary for the conduct of the trial.

In the United States (US), labeled and packaged binimetinib and encorafenib will be supplied to investigational centers by Array BioPharma. Cetuximab supply within the US will be supplied either locally or by Array BioPharma. Array BioPharma will employ a licensed company specializing in packaging, labeling, and distribution of investigational medicinal products.

In Japan (JAP), labeled and packaged binimetinib, encorafenib and cetuximab will be supplied to investigational centers by Array BioPharma via a licensed company specializing in packaging, labeling, and distribution of investigational medicinal products via a warehouse facility located in Japan.

6.1. SOURCE, PRESENTATION AND COMPOSITION OF INVESTIGATIONAL PRODUCT(S) AND ASSOCIATED PRODUCT(S)

